**Table 24. List of Analytes**

Chemistry	Hematology	Urinalysis	Coagulation	Other Labs
Sodium	Erythrocytes	Specific gravity	PT	Pregnancy test a
Potassium	Hemoglobin	pH	PTT	Serology (HepB, HepC)
Bicarbonate	Hematocrit	Blood	INR	
Or	MCV	Protein	Fibrinogen	MRD (for subjects with <5% blasts in bone marrow; Groups 1 and 2)
Total CO 2	Platelets	Glucose	AT III	
Chloride	WBC Differential	Bilirubin		
Total protein	Total Neutrophils	Ketones		
Albumin	Seg. Neutrophils	Microscopic exam		
Adjusted	Lymphocytes	(performed at the discretion of the investigator)		
Calcium	Atypical Lymphocytes			
Magnesium	Monocytes			
Phosphorus	Bands/Stabs			
Glucose	Eosinophils			
Creatinine	Basophils			
Total bilirubin	Blasts			
ALP	Myeloblasts			
AST	Monoblasts			
ALT	Megakaryoblasts			
GGT	Promyelocytes			
Amylase	Myelocytes			
Lipase	Metamyelocytes			
CRP	Nucleated RBC			
LDH	Immature			
Uric Acid	Granulocytes			
Ferritin				

ALP = alkaline phosphatase; ALT = alanine aminotransferase; anti-HBc = Hepatitis B core antibody; AST = aspartate aminotransferase; AT III = Antithrombin III; CRP = C-reactive protein; **GGT = gamma-glutamyl transferase**; HepBsAg = hepatitis B surface antigen; HepCAB = hepatitis C antibody; INR = international normalize ratio; LDH = lactate dehydrogenase; MCV = mean corpuscular volume; PT = prothrombin time; PTT = partial thromboplastin time; WBC = white blood cell

a Serum pregnancy test will be performed for all females unless surgically sterile or ≥ 2 years postmenopausal.

Additional procedures (eg collection of an unscheduled blood sample to measure cytokine levels) deemed necessary as part of standard of care or as required by local laws and regulations may be performed at the investigator's discretion.

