#### **7.5.2        Phenotyping and Genotyping of AML Blasts and Assessment of MRD**

The term MRD refers to the 'occult' low amount of leukemia that may persist during remission in the absence of clinical or hematological evidence of disease. Recently, the level of MRD was established as a prognostic factor that predicts relapse.

MRD detection in AML using PCR based techniques for molecular markers is applicable only in a minority of cases. Immunophenotypical detection of MRD is analyzed in one of 2 ways: (a) leukemia-associated immunophenotype (LAIP) or (b) deviation from normal maturation. The first is based upon the presence of so called LAIPs, which are unusual or aberrant immunophenotypes that distinguish leukemic cells from normal hematopoietic cells. The second, deviation from normal maturation, relies upon immunophenotypic deviation relative to normal bone marrow maturation. In this study, we will utilize the deviation from normal maturation method of MRD detection, as determined by a board-certified hematopathologist. This method relies upon cross-lineage antigen expression (eg, the expression of lymphoid markers on myeloid cells), the asynchronic antigen expression (eg, the coexpression of early markers with mature myeloid markers), overexpression of antigens (eg, relatively high expression levels of particular myeloid or lymphoid markers), and/or ectopic expression (eg, the expression of particular antigens that normally are not expressed on hematopoietic cells). At diagnosis, the immunophenotypic deviation relative to normal bone marrow maturation is identified, and this diagnostic immunophenotype is used as a starting point to follow the discrete population having an immunophenotype different from normal bone marrow. Deviation from normal maturation has an advantage over the LAIP method of MRD detection in that it has improved sensitivity through population identification and it is less sensitive to immunophenotypic instability.

The method of MRD detection is quite easy to perform and is sensitive, with a detection ability of approximately 1 malignant cell among 1,000 to 10,000 normal cells by flow cytometry, but it requires detailed immunophenotypical knowledge of normal bone marrow cell differentiation. Bone marrow after different courses of therapy, stem cell transplants, and sequential follow-up bone marrow sampling have been used for MRD assessment.

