In this study, MRD assessments [REDACTED] [REDACTED]. For subjects enrolling in Group 1, bone marrow sample for phenotyping and genotyping of AML blasts at baseline is only required for central testing; local testing is optional. [REDACTED]

[REDACTED]. For subjects enrolling in Group 4 and 5, central testing is not required; local testing is optional.

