5.4 Endpoints

Treatment-Emergent Adverse Event (TEAE)

Events categorized as Adverse Events (AEs) starting on or after first dose of investigational product as determined by "Did event start before first dose of investigational product (enter response based on earliest administration of [REDACTED]
[REDACTED], or AMG330, whichever occurred first)" equal to "No" or missing on the Events eCRF and up to 30 days after last administration of AMG330 or end of study date, whichever is earlier. Disease related events (DREs) will be included in the TEAE summary.

The severity of each adverse event will be graded using the CTCAE version 4.0. Adverse events will be coded using MedDRA. For CRS events, revised grading system will be used as per protocol ([Lee et al. 2014](#)).

Treatment-Related AE

A treatment-related AE is any treatment-emergent AE that per investigator review has a reasonable possibility of being caused by the investigational product.

Dose Limiting Toxicities (DLT)

DLT will be determined by "Is this event a Dose Limiting Toxicity (DLT)?" equal to "Yes" on the Events eCRF. Investigators will determine whether an adverse event qualifies as a DLT per protocol [Section 6.2.1.4](#).

Overall Response:

Overall response definitions are given below for different indications.

Group 1 in dose-escalation cohort / Group 4 (R/R AML)

Response is defined as any of the following:

Complete remission (CR), CR with incomplete recovery (CRI) or morphologic leukemia-free state (MLFS) (all according to Revised International Working Group [IWG] response criteria for AML), or CR with partial hematologic recovery (CRh).

Group 2 (MRD+ AML) (Primary)

Response is defined as CR without minimal residual disease (CRMRD-) or CRI without minimal residual disease (CRiMRD-). MRD- is defined as MRD threshold below 0.1% as per ELN recommendations ([Schuurhuis et al., 2018](#)).

Group 2 (MRD+ AML) (Exploratory)

Group 3 (MDS)

Response is defined as any of the following:

CR or marrow CR (all according to Revised IWG response criteria for MDS)

Group 5 and Group 1 in dose-expansion cohort (R/R AML)

Response is defined as any of the following: CRMRD-, CR, CRi, CRh, MLFS, PR.

Minimum Residual Disease (MRD) Response (All groups):

Minimum residual disease response is defined as MRD negative, indicating presence of leukemia cells to 0.1% or lower of white blood cells.

Duration of Response (DOR):

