6.1 Safety Analysis Set

Safety analysis set is defined as all subjects that are enrolled and receive at least 1 dose of AMG 330.

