8.3 Handling of Missing and Incomplete Data

The following imputation for missing or incomplete data will be performed if required: Incomplete adverse event and concomitant medication dates missing data will be imputed as described in [Appendix A](#).

Non-pharmacokinetic measurements (eg, biomarker data) that are below the lower limit of quantification will be considered equal to half of the lower limit of quantification for all analyses unless specified otherwise.

- Laboratory measurements that are below the quantification limits will be considered equal to the lower limit of quantification for all analyses unless explicitly noted otherwise.
- Biomarker data that are below the quantification limits will be considered equal to half of the lower limit of quantification for all analyses unless specified otherwise.
- PD concentrations that are below the quantification limits will be set to zero when engaging non-compartmental model to compute PD parameters.

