9.5.2 Analyses of Secondary Efficacy Endpoint(s)

The proportion of subjects with an overall response ([Section 5.4](#)) with corresponding exact 80% and 95% Confidence Intervals will be calculated using the Clopper-Pearson method ([Clopper and Pearson, 1934](#)) by cohort. The proportion of subjects who are event-free at 6 months with corresponding exact 80% CI will be calculated using the Clopper-Pearson method. The proportion of subjects with MRD response at the 0.1% threshold and the 0.01% threshold amongst subjects in the Safety Analysis Set will be summarized by cohort.

Listings indicating time to response, duration of response (DOR), and event-free survival will be produced for responders for each indication separately. For subjects in dose expansion cohorts, Kaplan Meier curves may be presented for event-free survival and overall survival with estimates for rates and 80% CI at selected weeks. DOR and time to response will only be analyzed for subjects who achieved an overall response.

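### MRD response is to be reported over all treated subjects in all groups, but MRD testing is set out only for Groups 1 and 2, so untested subjects in Groups 3 to 5 would count as non-responders

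*SAP*

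**What the plan says.** SAP 9.5.2, among the secondary efficacy analyses, summarises by cohort "The proportion of subjects with MRD response at the 0.1% threshold and the 0.01% threshold amongst subjects in the Safety Analysis Set". SAP 6.1 fixes that denominator: "Safety analysis set is defined as all subjects that are enrolled and receive at least 1 dose of AMG 330". Having an MRD test is not a condition of membership.

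SAP 5.4 heads the endpoint "Minimum Residual Disease (MRD) Response (All groups") and gives the rule "Minimum residual disease response is defined as MRD negative, indicating presence of leukemia cells to 0.1% or lower of white blood cells". In the same section, the primary Group 2 response definition puts MRD negativity strictly below 0.1%, as does Protocol 7.6.

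On who is tested, Protocol Table 24 has the entry "MRD (for subjects with <5% blasts in bone marrow; Groups 1 and 2"). Protocol 7.5.2.2 gives on-treatment sampling rules for Group 1 (triggered by blood blast findings or a suspected CR) and Group 2 (after every cycle), and for no other group. Protocol 7.5.2 adds: "For subjects enrolling in Group 4 and 5, central testing is not required; local testing is optional". Whole-blood MRD in Protocol Tables 12 and 13 is marked for Group 2 only, and the exploratory MRD objective in SAP 2.1 names Group 1 only.

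On sensitivity, Protocol 7.5.2 describes the method "with a detection ability of approximately 1 malignant cell among 1,000 to 10,000 normal cells by flow cytometry".

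**The concern.** The endpoint definition and denominator cover every treated subject, while the testing provisions cover two of the five groups. I found no visible rule for a treated subject without an MRD result. Taken literally, the proportion counts such a subject as not having responded. In a cohort where no one is tested, the table would show zero responders whatever the drug did, and a reader could take that for lack of activity in MDS.

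The 0.01% rate raises a separate question. It is only meaningful for samples whose assay can see down to 0.01%, and that is the best end of the only sensitivity range visible in the documents. If assay depth varied between samples, the 0.01% rate would partly depend on it.

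The third matter is the boundary. SAP 5.4 includes a value of exactly 0.1% as negative in one definition and excludes it in another.

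**Working it through.** **Plan's own figure.** The planned total in SAP 3.2 is 70 (Group 1 escalation) + 36 (Group 2) + 36 (Group 3) + 90 (three expansion cohorts of up to 30) + 24 (Groups 4 and 5) = 256, which matches the stated figure of about 256. With 6 rather than 12 subjects in Group 5 it is 250.

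**Who has MRD testing set out.**
- Group 1: up to 70 + 30 = 100
- Group 2: up to 36 + 30 = 66
- Together: 166/256 = 65%

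**Who does not.**
- Group 3: up to 36 + 30 = 66, or 66/256 = 26%
- Groups 4 and 5: about 24
- Together: 90/256 = 35%

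**An untested cohort.** A Group 3 expansion cohort of 30 with no MRD test would show 0/30. SAP 9.5.2 attaches no interval to this proportion. If the exact method in SAP 9.1 were applied, the upper 80% limit would be 1 − 0.10^(1/30) = 7.4%, and the upper 95% limit 1 − 0.025^(1/30) = 11.6%. Such an interval would look informative although nothing had been measured.

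**A partly tested cohort.** Let p be the true MRD-negative rate and f the share tested among subjects who would be negative. The reported rate is p × f. With p = 20% (assumed), it is 0%, 5%, 10%, 15% and 20% for f = 0, 25, 50, 75 and 100%. The documents give no f, so this shows a range and is not an estimate.

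**Groups 1 and 2 at 0.1%.** The summary is by cohort, so zeros in Groups 3 to 5 cannot dilute these rates. A Group 1 subject with 5% or more marrow blasts is outside the Table 24 condition and cannot be MRD negative, so counting that subject as a non-responder is correct. Group 2 is sampled after every cycle.

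**Sensitivity.** 1/1,000 = 0.1% and 1/10,000 = 0.01%. The 0.1% threshold is therefore resolvable across the stated range, with no margin at the weaker end. The 0.01% threshold is resolvable only at the stronger end. A negative result from an assay with a limit of 0.1% is compatible with any level below 0.1%, so it does not say on which side of 0.01% the sample lies.

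**Boundary.** At a value of exactly 0.1%, the all-groups rule gives MRD negative and the Group 2 rule gives not negative. A Group 2 subject at that value would be an MRD responder but not an overall responder.

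**The case against.** The strongest reply has several parts.

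- **Zero in Group 3 is an inference.** No text says a cohort without data must be displayed as 0/n. Protocol 7.5.1 names MRD for subjects with under 5% blasts without limiting it by group, so some Group 3 results may exist. MDS activity has its own response definition. This stands as a condition: the 0/n result holds only where no test is done.
- **The sentence on Groups 4 and 5 is partly out of context.** It follows redacted text and a sentence on baseline phenotyping, so its reach to on-treatment MRD is likely but not certain. SAP 9.1 also defers additional analyses for these groups to a supplemental plan. CR without MRD is a response category for Group 5, but plain CR counts as a response too, so a missing MRD test does not change that subject's overall response.
- **Assay details are redacted.** Central-assay and next-generation sequencing details are blacked out, and the exploratory Group 2 definition is not visible. The absence of a visible 0.01% rule cannot be held against the plan. The sensitivity point is therefore conditional.
- **The analysis is descriptive.** No test, sample size or decision rule uses it.

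Three stronger readings are tempting and are not supported. The first is that all the MRD rates will reflect testing and assay limits rather than disease. The working above shows that this fails for the 0.1% rates in Groups 1 and 2. The second is that the 10^-3 minimum sensitivity in Protocol 7.5.2.1 governs on-treatment samples. That section concerns Group 2 screening, while Sections 7.5.2.2 and 7.7 send on-treatment MRD to central laboratories. The third is that the imputation rule in SAP 8.3, "Biomarker data that are below the quantification limits will be considered equal to half of the lower limit of quantification", forces a shallow assay to give no response at 0.01%. That would require the quantification limit to equal the stated detection sensitivity and an imputed number to decide MRD status. The documents say neither; Protocol 7.5.2 has a hematopathologist make the MRD determination.

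**Conclusion.** The mismatch between denominator and testing is real, and confined to Groups 3, 4 and 5: up to 90 of 256 planned subjects, of whom 66 have MDS. Its effect ranges from none, if everyone in those groups is in fact tested, to a reported 0/n where no one is. The share tested is not stated.

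The 0.01% point is conditional on some samples being assayed with a detection limit above 0.01%, which the redactions leave open. The boundary conflict is certain but touches only values at exactly 0.1%.

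The conclusion assumes that SAP 9.5.2 is applied as written, with no unseen rule for untested subjects. Because the proportion is descriptive, the consequence is a possibly misleading table, and no trial decision is affected. It is worth correcting because the table sits among the secondary efficacy results and the correction is small.

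**What to change.** In SAP 5.4 and 9.5.2:

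1. Limit the MRD response proportion to Groups 1 and 2. For Groups 3, 4 and 5, list any MRD results with the number tested and give no proportion over all treated subjects.
2. Keep the Safety Analysis Set as denominator for Groups 1 and 2, and show the number tested beside it.
3. Report the 0.01% rate only for samples with a documented detection limit of 0.01% or lower. Count the others as not evaluable at that threshold and show how many there are.
4. Use one boundary, below 0.1%, throughout.

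The cost is SAP wording and one extra column in the tables, with no new sampling. The drawback is fewer evaluable subjects at 0.01%.

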9.5.3 Analyses of Exploratory Efficacy Endpoint(s)

The following statistical analyses will be considered exploratory and will be performed by clinical biomarker group in Department of Translational Medicine only when deemed appropriate. Relationships between changes in tumor dynamics and above biomarkers of interest listed as exploratory endpoints will be explored. Changes in expression levels of biomarkers and their relationship to dose may also be explored. Summary statistics over time will be provided and graphical presentations may be used. The relationship between

AMG 330 exposure and PD effects and related biomarkers in blood, or tumor specimens and/or AMG 330 exposure and clinical outcomes (eg, tumor response) will be also explored if deemed appropriate. Details of analysis will be provided in a Contributing Scientific Report for exploratory biomarker analysis. Pharmacodynamic (PD) biomarkers for AMG 330 mechanism of action (Depletion of LSCs, Lymphocyte counts, CD33+ monocytes ,T cells, T cell activation (including T cell subsets), Other immune subsets,

[REDACTED]

[REDACTED]

[REDACTED]

[REDACTED]

9.6 Safety Analyses

9.6.1 Analyses of Primary Safety Endpoint(s)

Unless otherwise specified, statistical analyses on safety endpoints will be done using subjects from the Safety Analysis Set, which includes subjects that are enrolled and received at least 1 dose of AMG 330. Unless otherwise noted, treatment groups will be defined based on the planned doses for Cycle 1.

9.6.2 Analyses of Dose Limiting Toxicities

The analysis of Dose limiting toxicities (DLT) will be based on the DLT Evaluable Analysis Set. A listing and summary of the subject incidence of dose limiting toxicities (DLT) will be provided.

9.6.3 Adverse Events and Disease-related Events

The Medical Dictionary for Regulatory Activities (MedDRA) version 24.1 or later will be used to code all events categorized as adverse events and disease-related events to a system organ class and a preferred term.

The subject incidence of adverse events (including disease related events) will be summarized for all treatment-emergent adverse events, treatment-related adverse events, serious adverse events (SAEs), grade 3 and above adverse events, adverse events leading to withdrawal of investigational product, adverse events leading to interruption of investigational product and fatal adverse events by system organ class, preferred term, and worst grade. In addition, SAEs and grade 3 and above adverse events will be summarized by preferred term in descending order of frequency.

The severity of each adverse event will be graded using Common Terminology Criteria for Adverse Events (CTCAE) version 4.0 criteria with the exception of cytokine release

syndrome (CRS), which will be graded using the criteria referenced in the publication by [Lee et al \(2014\)](#).

Subject incidence of events of interest (standardized MedDRA queries and/or Amgen customized queries) will also be summarized according to their categories and preferred term and worst grade. CRS will be summarized by grade and symptom.

TEAE summaries will be provided both by cohort and by overall groups.

9.6.4 Laboratory Test Results

Clinical chemistry, hematology, and urinalysis data will be listed and reviewed for each subject for DLRM. Values outside the normal laboratory reference ranges will be flagged as high or low on the listings.

In interim, primary and final analyses, depending on the size and scope of changes in selected laboratory data, summaries of selected laboratory data over time and/or changes from baseline over time may be provided. Tables of maximum shifts from baseline for selected laboratory values may also be provided. Unscheduled assessments will be included in these summaries.

9.6.5 Vital Signs

Vital signs data will be listed and reviewed for each subject for DLRM.

In interim, primary and final analyses, depending on the size and scope of changes, summaries of vital signs (resting systolic/diastolic blood pressure, heart rate, respirations and temperature) data over time and/or changes from baseline over time may be provided. Unscheduled assessments will be included in these summaries.

9.6.6 Physical Measurements

The change in weight from baseline to each scheduled assessment time point will be summarized.

9.6.7 Electrocardiogram

All on-study electrocardiogram (ECG) data (QRS, QT, QTc, RR, and PR intervals) will be listed.

Where multiple 12-lead ECG measurements are taken at the same assessment (they are planned to be recorded in triplicate <30 seconds apart) the mean value will be calculated and used in the analysis. Their primary approach will include all measurements taken at the assessment for the derivation of the mean value. The baseline ECG is defined as the

mean of all pre-dose assessments; the mean of values in a triplicate should be calculated before taking the mean of the triplicate averages.

In the event of extreme outlier readings, an additional sensitivity analysis will be conducted where the outlier measurement is excluded from the derivation of the mean for that assessment. The criteria used to define an outlier measurement will be determined based upon inspection of the data.

For pre- and post- dose ECG measurements, unscheduled ECG measurements taken up to 5 minutes after the last assessment of a triplicate will be included in the average for a time point. Where an ECG is missing within a triplicate, all available data will be averaged for that time point.

Summaries over time and/or changes from baseline over time will be provided for all 12-lead ECG parameters. The analysis of Fridericia's (QTcF) QT correction and Bazett's (QTcB) QT correction will be performed.

Subjects will be categorized into the following groups per their maximum change from baseline in QTcF and QTcB. Unscheduled assessments will be included in the determination of the maximum change.

- <= 30 msec
- 30 – 60 msec
- >60 msec

The number and percentage of subjects in each group will be summarized. A listing of the subjects with > 60 msec change from baseline in QTcF and QTcB will be provided.

Subjects will also be categorized into the following groups per their maximum post baseline QTcF and QTcB. Unscheduled assessments will be included in the determination of the maximum post baseline value.

- <= 450 msec
- > 450 – 480 msec
- > 480 – 500 msec
- > 500 msec

The number of subjects in each group will be summarized for each dosing group. A listing of the subjects with > 500 msec post baseline in QTcF and QTcB will be provided.

